7.2. Serious Adverse Events for expedited reporting

SAEs occurring within 1 week from the date of the colonoscopy (and not listed as 'expected' as defined above) will always be reportable to the ENDCaP-C Study Office on an SAE form. The assessment of relatedness to the study intervention is a clinical decision and will be based on all available information at the time. This applies for both the baseline and follow-up colonoscopy.

SAEs outside of this timeframe can also be reported if it is the opinion of the Investigator that there is a possible causal relationship to another aspect of the study. An assessment of relatedness and expectedness will be undertaken by the Chief Investigator (or delegated Clinical Coordinator). All SAEs will be followed-up until the event has resolved or a decision has been taken for no further follow-up.

7.3. Reporting SAEs

All SAEs must be recorded on the SAE Form and faxed to the ENDCaP-C Study Office on [name] within 24 hours of the research staff becoming aware of the event.

The Principal Investigator (or other nominated clinician) has to assign seriousness and causality to the SAE as part of the reporting process.

For each SAE, the following information will be collected:

- full details in medical terms with a diagnosis, if possible
- its duration (start and end dates; times, if applicable)
- action taken
- outcome
- causality, in the opinion of the investigator*
- whether the event would be considered expected or unexpected*

^{*}Assessment of causality must be made by a doctor. If a doctor is unavailable, initial reports without causality assessment should be submitted to the BCTU by a healthcare professional within 24 hours, but

must be followed up by medical assessment as soon as possible thereafter, ideally within the following 24 hours.

The local investigator and others responsible for patient care should institute any supplementary investigations of SAEs based on their clinical judgement of the likely causative factors and provide further follow-up information as soon as available. If a participant dies, any post-mortem findings must be provided to the BCTU. The BCTU will report all deaths to the DMEC for continuous safety review.

7.4. Notification of deaths

All deaths will be reported to the BCTU on the SAE Form irrespective of whether the death is related to disease progression or an unrelated event. If a participant dies, any post-mortem findings must be provided to the BCTU with the SAE form. The BCTU will report all deaths to the DMEC for continuous safety review.

7.5. Pharmacovigilance responsibilities

Local Principal Investigator (or nominated individual in PI's absence):

- Medical judgement in assigning seriousness and causality to SAEs.
- To fax SAE forms to BCTU within 24 hours of becoming aware, and to provide further follow-up information as soon as available.
- To report SAEs to local committees if required, in line with local arrangements.
- To sign an Investigator's Agreement accepting these responsibilities.

Chief Investigator (or nominated individual in CI's absence):

- To assign causality and expected nature of SAEs where it has not been possible to obtain local assessment
- To review all events assessed as SAEs in the opinion of the local investigator

Birmingham Clinical Trials Unit:

- To prepare annual safety reports to main REC and TSC.
- To prepare SAE safety reports for the DMEC at a minimum of 12-monthly intervals.
- To report all fatal SAEs to the DMEC for continuous safety review.

Study Steering Committee (TSC):

- To provide independent supervision of the scientific and ethical conduct of the study on behalf of the Study Sponsor and funding bodies.
- To review data, patient compliance, completion rates, adverse events (during treatment and up to end of follow-up).
- To receive and consider any recommendations from the DMEC on protocol modifications.

Data Monitoring & Ethics Committee (DMEC):

- To review overall safety and morbidity data to identify safety issues which may not be apparent on an individual case basis
- To recommend to the TSC whether the study should continue unchanged, continue with protocol modifications, or stop.

7.6. Notification of Serious Breaches of GCP and/or the protocol

A "serious breach" is a breach which is likely to effect to a significant degree:

- (a) the safety or physical or mental integrity of the participants of the study; or
- (b) the scientific value of the study.

The BCTU on behalf of the Sponsor shall notify the REC in writing of any serious breach of:

- (a) the conditions and principles of GCP in connection with the study; or
- (b) the protocol relating to the study, as amended from time to time, within 7 days of becoming aware of that breach.

The Sponsor will be notified immediately of any case where the above definition applies during the study conduct phase.

8. DATA HANDLING AND RECORD KEEPING

It will be the responsibility of the Principal investigator to ensure the accuracy of all data entered in the CRFs. The ENDCaP-C Delegation & Signature Log will identify all those personnel with responsibilities for data collection.

8.1. Data management and validation

Data should be collated directly from the patient (for Quality of Life questionnaires) or from the patient hospital notes using the ENDCaP-C case report forms. Within the ENDCaP-c study, source data is the participants' medical notes generated and maintained at site.

Data will be collected via paper CRFs; paper forms should be sent to the ENDCaP-C Study Office for central input. Data validation is built into the database, so that range, date and logic checks are performed at the point of data entry.

Paper CRFs must be completed, signed/dated and returned to the ENDCaP-C Study Office by the Investigator or an authorised member of the site research team (as delegated on the ENDCaP-C Study Signature & Delegation Log) as soon as possible. Data reported on each CRF should be consistent with the source data or the discrepancies should be explained. If information is not known, this must be clearly indicated on the CRF. All missing and ambiguous data will be queried. All sections on the CRFs are to be completed.

The ENDCaP-C Study office will request any CRF not received within 1 week of the due date.

Email and letter reminders will be sent to the investigator and research coordinator for missing CRFs; Data Clarification Forms (DCFs) will be sent to request missing data or to resolve data inconsistencies.

Once completed, original CRFs and DCFs will be sent to the ENDCaP-C Study Office and copies retained at site to be filed in the Investigator Site File.

8.1.1 Confidentiality of personal data

All data will be handled in accordance with the UK Data Protection Act 1998.

Participants will give their explicit permission for a copy of their consent form, which contains their full name, to be sent to the ENDCaP-C Study Office to be sent a copy. This will be used to perform in-house monitoring of the consent process.

Participants' names will not be written on any CRF. Participants' month and year of birth, last four digits of their hospital number and study identification number will be used for identification. The exception will be the registration form where participants' name, date of birth and hospital number will be recorded in full.

8.2. Definition of the End of Study

The end of the study for regulatory purposes is defined as the date of the last visit of the last patient undergoing protocol based treatment and collection of associated data. Within ENDCaP-C, this is once the last participant has undergone the late reference procedure at4-12 months. This will allow sufficient time for the completion of protocol procedures, data collection and data input.

Follow-up at 4-12 months post-study entry will constitute the end of the non-interventional phase of the study. It is possible that the patient will be eligible to continue with further follow up in another study and consent for this possibility will be obtained along with consent to participate in the ENDCaP-C study.

9. DATA ACCESS AND QUALITY ASSURANCE

9.1. Confidentiality of personal data

Personal data and sensitive information required for the ENDCaP-C Study will be collected directly from study participants and hospital notes. Participants will be informed about the transfer of this information to the ENDCaP-C Study Office at the BCTU and asked for their consent. The data will be entered onto a secure computer database indirectly from paper forms by BCTU staff.

All personal information received in paper format for the study will be held securely and treated as strictly confidential according to BCTU policies. All staff involved in the ENDCaP-C Study (clinical, academic, BCTU) share the same duty of care to prevent unauthorised disclosure of personal information. No data that could be used to identify an individual will be published. Data will be stored on a secure server at Birmingham Clinical Trials Unit (BCTU) under the provisions of the Data Protection Act and/or applicable laws and regulations.

9.2. In-house Data Quality Assurance

9.2.1 Monitoring and Audit

Investigators and their host Trusts will be required to permit study-related monitoring and audits to take place by the ENDCaP-C Study Office, providing direct access to source data and documents as requested. Trusts may also be subject to inspection by the Research and Development Manager of their own Trust and should do everything requested by the Chief Investigator in order to prepare and contribute to any inspection or audit. Study participants will be made aware of the possibility of external audit of data they provide in the participant information sheet.

9.2.2 Statistical monitoring throughout the study

Real-time reports will be available to research staff indicating missing test data for all participants at that centre. This will be supplemented by regular reminders from the Study Office for incomplete data. The study statistician will regularly report on recruitment, compliance and completeness of verification to the Steering Committee.

9.3. Independent Trial Steering Committee

The TSC provides independent supervision for the study, providing advice to the Chief and Co-Investigators and the Sponsor on all aspects of the study and affording protection for patients by ensuring the study is conducted according to the MRC Guidelines for Good Clinical Practice in Clinical Trials.

If the Chief and Co-Investigators are unable to resolve any concern satisfactorily, Principal Investigators, and all others associated with the study, may write through the Study Office to the chairperson of the TSC, drawing attention to any concerns they may have about the possibility of particular side-effects, or of particular categories of patient requiring special study, or about any other matters thought relevant.

9.4. Data Monitoring and Ethics Committee

During the study, interim analyses of safety and outcome data will be supplied, in strict confidence, to an independent Data Monitoring and Ethics Committee (DMEC) along with any other analyses that the committee may request. Further details of DMEC functioning are presented in the DMEC Charter.

9.5. Long-term storage of data

All records created by following trial procedures and all documents listed in guidance relating to the conduct of the trial must be retained and archived.

Archiving will be authorised by the BCTU on behalf of the Sponsor following submission of the end of study report.

Principal Investigators are responsible for the secure archiving of essential study documents and source documents (e.g. signed Informed Consent Forms, Investigator Site Files, participants' hospital notes, copies of CRFs etc.) (for their site) as per their NHS Trust policy. All essential documents will be archived for a minimum of 15 years after completion of study.

Destruction of these documents will require authorisation from the BCTU on behalf of the Sponsor.

10. OUTCOME MEASURES

10.1. Protection from bias

The generalisability of the study will be assured by aiming to recruit a consecutive sample of patients attending for routine surveillance who fall within the high risk category. We will collect information on risk factors in all study patients and investigate whether the diagnostic value of methylation varies according to patient characteristics.

Misclassification bias can occur in test accuracy studies where the reference standard test is inaccurate. Whilst we are ensuring the initial colonoscopy is a routine surveillance procedure to ensure the study is pragmatic and will address the incremental value of methylation over and above standard current practice, the reference standard colonoscopy will be of the highest quality possible, utilising dye spray to increase dysplasia detection and restricting to experienced, nominated colonoscopists at each site. In addition this colonoscopy will occur 4-12 months after the initial colonoscopy, which will increase the chances of finding dysplasia that was initially not detected (i.e. identifying patients with false negative initial histology). Whilst there is a risk that new dysplasia may develop during this period, we have chosen a time period to minimise this risk, which should not introduce bias as it should be equal in both methylation test positives and negatives. Long term follow up of this cohort of patients will be undertaken, to assess late conversion rate to neoplasia. This will be undertaken outside of this study.

We have elected only to undertake reference standard colonoscopies in a sample of methylation test negatives. As this sample will be chosen randomly without matching it should be representative of all test negatives, and the results not suspect to partial verification bias.

10.2. Outcome Measures

10.2.1 Primary Outcome Measures

The primary outcome measures are:

- The occurrence of dysplasia in mucosal biopsies taken at follow up colonoscopy at 4-12 months in patients demonstrating hypermethylation (the positive predictive value)
- The ability of hypermethylation to discriminate between patients with and without dysplasia in mucosal biopsies taken at follow up colonoscopy at 4-12 months (the diagnostic odds ratio)

10.2.2 Decision tool for a positive methylation

The decision for a patient to be classified whether they are a test positive will be based on the model equation developed from Module 1. Due to some biomarkers tendency to fail amplification, it was decided by the Study Management Group that for the accuracy of the prediction of classifying a patient to be test positive based on their methylation data, at least 3 out of 5 biomarkers were required to be successfully amplified.

Hence all possible combinations of model equations consisting of at least 3 or more biomarkers were produced from the Module 1 data. Altogether 16 different models were conducted to be used as a decision tool for a positive methylation.

10.2.3 Secondary Outcome Measures

The secondary outcome measures for the study are:

1. Complications from colonoscopy

10.3. Assessment and Follow up

Primary assessment will be undertaken by both histology and methylation analysis on the biopsy specimens (>/= 5 per patient). Follow up within the study will be by colonoscopy at 4-12 months after initial assessment, with repeat biopsy, and repeat methylation assessment. Long term follow up of this cohort of patients will be undertaken, to assess late conversion rate to neoplasia. This will be undertaken outside of this study. Consent will be taken to allow future linkage to patient data available in NHS routine clinical datasets, including primary care data (e.g. CPRD, THIN, QResearch), secondary care data (Hospital Episode Statistics; HES) and mortality data from the Office of National Statistics (ONS) through The Health and Social Care Information Centre and other central UK NHS bodies. The consent will also allow access to other new central UK NHS databases that will appear in the future. This will allow us to extend the follow-up of patients in the trial and collect long-term outcome and health resource usage data without needing further contact with the study participants. This is important as it will link a trial that may become a clinical standard of care to long-term outcomes that are routinely collected in clinical data, but which will not be collected during the follow-up period of the trial.

10.4. Assessment of efficacy

This study is designed as an accuracy study and thus there will be no direct measurement of the efficacy or effectiveness of the inclusion of methylation testing in a surveillance programme. As the results of the methylation test will not be routinely provided to clinicians or patients during the study, the outcomes of patients in this study will not be affected by the test. However, from the results of this study it will be possible to model the potential benefit of changing the surveillance programme. Primarily we expect that the benefits of the test will be in advancing the time point at which CAN is detected in a patient, increasing the chances of preventing cancer and curative therapy being possible.

We would propose that should methylation be found to advance the time of detection of CAN in this study, its full impact on health outcomes could be assessed as it is included in surveillance programmes using a stepped-wedge study design, as high quality baseline data is routinely collected in this well-defined patient group. This is outside the remit of the current protocol.

10.5. Assessment of safety

The key safety issue is the additional colonoscopy, performed at 4-12 months. This is up toupto 8 months earlier than the planned surveillance examination and is associated with a small but significant risk of bowel injury/perforation (0.1-0.3%). This risk must be balanced by the benefit of early detection of CAN and effective cancer prevention. The additional risk is only marginally above that incurred by each patient within the surveillance programme, who will undergo perhaps 10-20 examinations through their lifetime. All colonoscopies and incurred morbidity will be collected in a standardised fashion, and provided in IDMC reports. All colonoscopies will be undertaken by experienced colonoscopists, and follow up colonoscopies will be performed by named specialists at each site.

11. STATISTICAL CONSIDERATIONS

11.1. Sample size

Positive and negative predictive values of methylation for neoplasm will be computed from test positives and negatives respectively, sensitivities and specificities will be estimated adjusting for the sampling proportion in the test negatives (see 11.3).

Computation of the sample size is based on (1) records indicating that 4% are detected with dysplasia by histology from a high risk cohort; (2) an assumption that a further 4% are missed (assuming a detection rate of 50% for routine colonoscopy) of which (3) 50% will be detected by methylation testing (i.e. sensitivity=50%) which will (4) give false positive results in 5% free of dysplasia (i.e. specificity=95%). The sensitivity and specificity of methylation testing have been estimated to be 90% and 100% in retrospective samples, thus these figures are conservative.

The study is powered to have adequate power to show that the test is discriminatory (measured by having an odds ratio different from 1) and that the positive predictive value is high enough to be useful for identification of the high risk patients, being at least 15%. The clinical consequence of a positive test result would be a further colonoscopy, and we consider that detecting neoplasia in 1 in 7 selected for further investigation would be regarded a clinically useful yield. It is not feasible to power the study to show that the negative predictive value is low enough to identify a low risk group.

In our cohort of 1000 we estimate that there will be 80 with underlying dysplasia: 40 of these would be detected by histology from the initial biopsies, and 20 of the remaining 40 will be identified by the methylation test. Following the assumptions about test performance, the methylation test will thus give 46 false positive results (5% of the 920 without dysplasia) giving an expected positive predictive value of 30% (20 of 66). With the assumed test performance, a sample size of 66 test positives will have 87% power to show (in a one sample test) that the positive predictive value is over 15% with P<0.05.

We will additionally verify the status of 132 (twice as many) test negatives to obtain estimates of the sensitivity and specificity of the test (computed adjusting for the sampling fraction of test negatives). We would expect that these would include 3 found positive for dysplasia and 129 without dysplasia, which will provide over 90% power to show the diagnostic odds ratio is significantly (P<0.05) different from one. A specificity of 95% will be estimated with a confidence interval of less than 4% points.

11.2. Projected accrual and attrition rates

Active recruitment to the study will take place over approximately seventeen months. Over this time we intend to recruit a total of 1000 patients from up to 37 UK sites. An audit of UC patient activity at University Hospital Birmingham has already been performed in late 2012 to estimate throughput rates of potentially eligible patients for this study. This showed that around 5-6 patients per month are successfully medically treated for a UC relapse, who would thus be eligible for this study. The rate of two patients per month (33-

40% successfully recruited) seems a realistic target. A final point to note is that patients are eligible for up to a year after a disease relapse, as such they can be approached any time in this period when they routinely attend follow-up outpatient clinic, further increasing the achievability of these recruitment targets.

11.3. Statistical Analysis for Test Accuracy

Analysis for the primary outcome will estimate positive and negative predictive values of methylation as the proportion of those methylation positive at the initial colonoscopy that are detected with CAN at the reference colonoscopy, and the proportion methylation negative that are free of CAN at the reference colonoscopy, respectively. The diagnostic value of the test will also be summarised as a diagnostic odds ratio, and values of sensitivity and specificity will be computed from predictive values utilising knowledge of the prevalence of CAN and the sampling fraction in those methylation negative. All estimates will be presented with 95% confidence intervals.

The baseline characteristics of the patients enrolled in the study will be examined and planned subgroup analyses will be undertaken using generalised estimating equation logistic regression models. Subgroup analyses are limited by statistical power and will be interpreted with appropriate caution.

Analyses for the primary outcome comparing results of the reference colonoscopy with methylation testing will only be made at a patient level. Although multiple samples are available from each, they cannot be matched at a lesion level as they are based on separate colonoscopic examinations. A patient will be defined as methylation positive if they are positive for any sample, likewise they will be defined as CAN positive if they are histology positive for any sample.

Analysis of the secondary objective of the diagnostic value of methylation will compare results from the same examination, and both lesion and patient level analyses will be possible. Lesion based analyses will take into account repeated samples from individuals using robust standard errors and hierarchical model structures.

We will also investigate the correlation of methylation in biopsies with methylation of proteins detected in serum and of proteins detected in faecal samples.

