2. OBJECTIVES AND OUTCOMES

2.1. Objectives

ENDCaP-c is multi-centre cohort study with the following objectives:

Primary objective:

• To estimate prospectively the ability of the methylation assay to detect pre-cancerous lesions (dysplasia) missed by histology within a surveillance programme for colitis associated neoplasia (CAN).

Secondary objectives:

- To estimate the incremental accuracy of methylation testing over histology within a CAN surveillance programme and gain experience of its applicability in the clinical setting.
- To evaluate the feasibility of testing for hypermethylation of secreted Wnt antagonists in serum and faecal samples, and if feasible, to assess their accuracy

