6.3. Early Reference Standard (see 3.6, Study Schema)

The early reference standard will be the histological analysis obtained from the standard surveillance colonoscopy at trial entry as detailed above.

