6.4. Late Reference Standard (see 3.6, Study Schema)

All histologically negative patients with positive methylation status (test positives) will be identified by the ENDCaP-C Study Office and will be invited to undergo early repeat colonoscopy. Twice as many histologically negative patients that have negative methylation status will be randomly selected without matching (test negatives) by the ENDCaP-C Study Office and also will be invited to undergo early repeat colonoscopy. The late reference standard colonoscopy will be undertaken 4-12 months after the standard colonoscopy, blinded to methylation status. This reference assessment will be standardised using dye spray and targeted biopsy to maximise dysplasia detection, and should be performed by nominated, experienced colonoscopists at each site.

During this procedure, biopsy samples will be taken. As with the standard colonoscopy at trial entry, our requirements are for two samples from the left side of the colon, two from the right side of the colon and one from the rectum. We do not object to additional biopsies being taken and sent to us if this is preferred at a site. Each biopsy will involve two "bites" from the mucosa using a spiked endoscopy forceps as is current standard practice.

Biopsy samples should be embedded in paraffin and processed and analysed as per local practice. It is important that biopsies from different sites (left, right and rectum) should not be embedded into the same block and so we expect a minimum of THREE blocks, one per site. If this is not possible or unavoidable, guidance on the how to identify the appropriate biopsies must be provided.

The ENDCaP-C Study Office will send out instructions on sample requirements to all participating centres.

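### Section 11.3 matches the secondary objectives to the wrong analyses: same-examination histology cannot show accuracy added to histology, and a correlation is not serum or stool accuracy

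*Protocol*

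**What the plan says.** Protocol section 2.1 lists two secondary objectives. The first is "To estimate the incremental accuracy of methylation testing over histology within a CAN surveillance programme", together with gaining experience of the test in clinical use. The second is the feasibility of serum and faecal testing, "and if feasible, to assess their accuracy".

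Section 11.3 gives the matching analyses:

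- For biopsies: "Analysis of the secondary objective of the diagnostic value of methylation will compare results from the same examination", at lesion and patient level.
- For serum and stool: "We will also investigate the correlation of methylation in biopsies with methylation of proteins detected in serum and of proteins detected in faecal samples".

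Section 3.1 uses the label diagnostic value for the comparison of methylation with histology from the first colonoscopy. Section 6.3 defines the reference there: "The early reference standard will be the histological analysis obtained from the standard surveillance colonoscopy at trial entry". Section 2.1 lists no objective called diagnostic value.

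The primary comparison (sections 3.1, 6.4 and 11.3) is different. It takes patients with negative baseline histology, invites all methylation positives and twice as many randomly chosen methylation negatives to a colonoscopy at 4-12 months, and uses that histology as the reference. Blood and stool are collected at this second visit only, from patients who agree (sections 6.4.1 and 6.4.2).

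**The concern.** Incremental accuracy asks what methylation finds that histology missed. If histology from the same examination is the reference, histology is perfect by definition, and every extra patient flagged by methylation is a false positive. A missed dysplasia that methylation picks up lowers apparent specificity instead of raising sensitivity.

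The sentence in section 11.3 can be read in two ways. Either it is the analysis of the incremental objective, and the reference is wrong for it. Or it serves an objective that section 2.1 does not list, and the listed one has no analysis named for it. Both readings need an amendment.

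For serum and stool, a correlation with biopsy methylation says how far two methylation measurements agree. It does not say how well either identifies dysplasia. Section 11.3 also refers to "correlation of methylation in biopsies with methylation of proteins detected in serum", whereas section 6.2 defines a DNA methylation panel.

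At stake is what gets reported under each secondary objective: an agreement result where added detection was promised, and a correlation where sensitivity and specificity were promised.

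**Working it through.** **Inputs (section 11.1).** Cohort of 1000; 80 with underlying dysplasia, of whom 40 are found by baseline histology; methylation finds 50% of the 40 missed; 5% false positives among the 920 without dysplasia; 132 test negatives verified, 3 of them expected to have dysplasia.

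**The plan's own figures.**
- True positives 0.5 × 40 = 20; false positives 0.05 × 920 = 46; total 66; positive predictive value 20/66 = 30.3%.
- Histology-negative test negatives: 1000 − 40 − 66 = 894. Expected dysplasia among 132 of them: 132 × 20/894 = 2.95, that is 3.
- Power for a predictive value above 15% with n = 66 and true value 30%, by the two-sided normal approximation: (√66 × 0.15 − 1.96 × √(0.15 × 0.85)) / √(0.30 × 0.70) = 1.13, giving 87.1%. The stated 87% is reproduced, and nothing below alters it.

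**Same-examination comparison.** The reference is baseline histology, so 40 are diseased and 960 are not.
- Histology scores 40/40 and 960/960 against itself.
- False positives for methylation: 20 + 46 = 66. Apparent specificity 1 − 66/960 = 93.1%, against the assumed 95%.
- Histology-or-methylation keeps 100% sensitivity and drops to 93.1% specificity. No result can favour adding methylation.

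**Reference of baseline or late-reference dysplasia.**

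| | Sensitivity | Specificity |
|---|---|---|
| Histology alone | 40/80 = 50% | 100% by construction |
| Histology or methylation | 60/80 = 75% | 874/920 = 95% |

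This result does not depend on how methylation performs in the 40 histology-positive patients.

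**As it would be estimated.** Weight for verified test negatives: 894/132 = 6.77. Missed dysplasia: 20 + 3 × 6.77 = 40.3. Total: 80.3. Histology alone 40/80.3 = 49.8%; combined 60/80.3 = 74.7%.

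The estimate leans on the few dysplasias found among test negatives. With k of them, the gain is 20/(60 + 6.77k):
- k = 1: 20/66.8 = 30 points
- k = 3: 20/80.3 = 25 points
- k = 6: 20/100.6 = 20 points

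**Serum and stool.** The correlation is computed from a biopsy-by-serum table that contains no histology. One assumed pattern shows that it does not determine accuracy. Let serum be positive in 33 of 66 biopsy positives and 0 of 132 biopsy negatives. Then phi = (33 × 132)/√(66 × 132 × 33 × 165) = 0.63. The 33 serum positives may include anything from none to all of the 20 dysplasias among biopsy positives. Serum sensitivity in the verified sample is therefore between 0/23 = 0% and 20/23 = 87%. With the weight, the upper end is 20/40.3 = 49.6%. The correlation is the same throughout.

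**The case against.** The strongest reply is that section 11.3 already delivers the increment. Its first paragraph analyses histology-negative patients against the late reference colonoscopy and adjusts for the sampling fraction. On planning figures that yields 20 of 40 missed dysplasias and a predictive value of 20/66. Sections 6.5 and 10.1 describe the design as measuring incremental value over current practice. Same-examination agreement is a legitimate analysis in its own right, and the protocol nowhere says that it measures the increment.

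This stands in part. A reader might infer that the trial cannot answer its secondary objectives, or that following section 11.3 yields zero or negative added value for a test that works. The documents do not support either, because the primary analysis supplies the needed data. What remains is that section 11.3 assigns the secondary objective another comparison and never states histology alone against histology-or-methylation.

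On serum and stool, accuracy is conditional ("if feasible, to assess their accuracy"), the samples are optional, and an analysis plan that is not shown may cover it. That is fair, but the only analysis stated is a correlation.

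A reader might also infer that the correlation will be inflated because the sampled patients were chosen on methylation. The documents do not establish this. Selection is on baseline methylation, methylation is measured again at the repeat visit, and section 11.3 does not say which measurement is used. They also give no serum-tissue agreement from which to size it.

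Finally, a reference that includes baseline histology makes histology alone 100% specific by construction. That is true of the remedy and must be stated with it.

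**Conclusion.** The point holds as a mismatch between stated analyses and stated objectives. The same-examination comparison counts all 66 expected histology-negative positives as errors, 20 of them wrongly. Against baseline or late-reference dysplasia, the same planning figures show sensitivity rising from 50% to 75%, with 46 false positives among 920. For serum and stool, the stated correlation leaves sensitivity undetermined.

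These sizes rest on the planning assumptions in section 11.1 and on late-reference histology identifying the dysplasia that baseline histology missed. The serum example is an assumed pattern used only to show that correlation does not fix accuracy. Any serum or stool accuracy would apply to patients with negative baseline histology and, because sampling is optional, rest on at most about 20 + 3 = 23 expected dysplasia cases. No sample size, power figure or primary analysis is affected.

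**What to change.** Amend section 11.3 as follows:

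- Estimate incremental accuracy as sensitivity and specificity of histology alone versus histology-or-methylation. The reference is dysplasia at baseline or at the late reference colonoscopy. Weight verified test negatives by the inverse of the sampling fraction (about 6.8 as planned; use realised counts).
- State that histology alone is 100% specific by construction under this reference.
- Keep the same-examination comparison, relabelled as concurrent agreement with histology.
- If serum and stool testing proves feasible, estimate sensitivity and specificity against same-visit late-reference histology with the same weights. State the restriction to histology-negative patients and the small expected number of cases. The correlation can stay as a descriptive addition.
- Replace methylation of proteins with DNA methylation.

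The cost is protocol or analysis-plan wording and a little extra analysis of data already planned. Weighted estimates will have wider intervals, because each dysplasia found among verified test negatives stands for nearly seven.
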